7.8.3 Vital signs

Only descriptive statistics by group and planned visit are planned for this section of the report. Clinically relevant findings in vital signs data were to be reported as AEs and will be analysed as part of AE analysis.

7.8.4 ECG

ECG data will not be listed but clinically relevant abnormal findings will be reported as AEs.

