dose:	Not applicable				

Proprietary confidential information © 2017 Boehringer Ingelheim International GmbH or one or more of its affiliated companies

Name of company: Boehringer Ingelheim		Tabulated Trial Protocol		
Name of finished product: Not applicable				
Name of active ingredient: BI 655130				
Protocol date: 18 Jan 2017	Trial number: 1368-0009		Revision date: 01 Aug 2017	
mode of admin.: Intravenous as 90 min infusion				
Comparator product 2: Matching placebo for BI 655130 ([REDACTED] solution for injection				
dose: Not applicable				
mode of admin.: Subcutaneous injection				
Duration of treatment: One day (single dose) for each treatment				
Criteria for pharmacokinetics:	(iv) single rising dose group Secondary endpoints: $AUC_{0-\infty}$, C_{max} , CL and V_{ss}			
	(sc) single dose group Secondary endpoints: $AUC_{0-\infty}$ and C_{max}			
Criteria for pharmacodynamics:	Not applicable			
Criteria for safety:	Primary endpoint to assess safety and tolerability of BI 655130 is the number [N (%)] of subjects with drug-related adverse events (AEs).			
Statistical methods: Descriptive statistics will be calculated for all endpoints. Dose proportionality of BI 655130 will be explored using a regression model. A 95% confidence interval (CI) for the slope will be computed.				

Proprietary confidential information © 2017 Boehringer Ingelheim International GmbH or one or more of its affiliated companies

FLOW CHART

(iv) Single rising dose group

Visit	Day	Time relative to first drug administration (planned time [h:min])	Approx. time (actual time [h:min])	Event and comment	PK _{blood} ⁴		Laboratory/ Urinalysis ³	Body Temperature	12-lead ECG	ECG monitoring	Vital signs (BP, PR)	Query on adverse events, concomitant therapies ⁹
1	-28 to -3			screening ¹			X		X		X	
	-3 to -1	-72:00	8:00	ambulatory visit			X ¹¹					
	-1	-12:00	20:00	admission to trial site								X
2	1	-2:00	6:00	randomization and pre-dose ²	X		X	X	X		X	X ⁵
		0:00	8:00	drug administration start of infusion						▲		
		0:30	8:30								X	
		1:00	9:00								X	
		1:30	9:30	▼ end of infusion ¹²	X			X	X		X	X ⁵
		2:00	10:00		X			X	X	▼	X	
		3:00	11:00		X						X	
		4:00	12:00	Lunch ⁶	X		X				X	X ⁵
		6:00	14:00					X	X		X	
		8:00	16:00		X						X	
	2	10:00	18:00	Dinner ⁶								
		12:00	20:00		X			X	X		X	X ⁵
		24:00	8:00	Breakfast ⁶	X		X	X	X		X	X ⁵
		28:00	12:00	Lunch ⁶								
		32:00	16:00				X				X	
		34:00	18:00	Dinner ⁶								X

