5.2.4 Electrocardiogram

5.2.4.1 12-lead resting ECG

Twelve-lead resting ECGs (I, II, III, aVR, aVL, aVF, V1 - V6) will be recorded using a computerised electrocardiograph at the time points given in the [Flow Chart](#).

In order to achieve a stable heart rate at rest and to assure high quality recordings at comparable resting phases, all ECGs will be recorded for a 10-sec duration after the subjects have rested for at least 5 min in a supine position. The site personnel will be instructed to assure a relaxed and quiet environment so that all subjects are at complete rest during the recordings. ECG assessment will always precede all other study procedures of the same time point (except blood drawing from an intravenous cannula which is already in place) to avoid impact of sampling on the ECG quality. Electrode placement will be performed according to the method of Wilson, Goldberger and Einthoven.

At all time points single ECGs will be recorded. All locally printed ECGs will be evaluated by the investigator or a designee. ECGs may be repeated for quality reasons (like alternating current artefacts, muscle movements, electrode dislocation). Additional (unscheduled) ECGs may be collected by the investigator for safety reasons. These ECGs are assigned to the prior scheduled time point. Unscheduled ECGs will not be included into the statistical analysis of interval lengths.

For the inclusion or exclusion (see [Section 3.3](#)) of a subject and for the assessment of cardiac safety during the study, the QT and QTcB values generated by the ECG machines or their manual corrections by the investigators will be used.

Abnormal findings will be reported as AEs (during the trial) or baseline conditions (at screening) if judged clinically relevant by the investigator. Any ECG abnormalities will be monitored carefully and, if necessary, the subject will be removed from the trial and will receive the appropriate medical treatment.

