7. STATISTICAL METHODS AND DETERMINATION OF SAMPLE SIZE

7.1 STATISTICAL DESIGN – MODEL

7.1.1 Objectives

The primary objective of this trial is to investigate the safety and tolerability of BI 655130 by using descriptive statistics for all endpoints comparing active dose groups to placebo. The primary endpoint is defined in [Section 5.2.1](#). Inferential statistics is not planned (as explained in Section 7.2).

The secondary objective is the exploration of the pharmacokinetics (PK) of BI 655130. Endpoints as specified in [5.5.1](#) will be analysed by descriptive statistics. $AUC_{0-\infty}$ and C_{max} for intravenous doses will be subjected to analysis of dose proportionality by use of the power model.

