7.2 NULL AND ALTERNATIVE HYPOTHESES

Safety and tolerability of 4 different dose groups of BI 655130 are to be determined on the basis of the investigated parameters in comparison to placebo. It is not planned to test any statistical hypotheses with regard to these variables in a confirmatory sense. Instead, they will be described in their entirety and evaluated by descriptive statistical methods.

Confidence intervals will be computed and will have to be interpreted in the perspective of the exploratory character of the study, i.e. confidence intervals are considered as interval estimates for effects.

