7.3.3 Safety analyses

Safety will be assessed for the endpoints listed in [Section 5.2.1](#). All treated subjects (that is, all subjects who received at least one dose of study drug), will be included in the safety evaluation. Safety analyses will be descriptive in nature and will be based on BI standards. No hypothesis testing is planned.

Treatments will be compared in a descriptive way. The placebo control group in the safety evaluation will consist of all placebo treated subjects, regardless of the dose group in which they were treated. The active treatment groups will be compared to the placebo group in a descriptive way. Tabulations of frequencies/proportions will be used for the evaluation of categorical (qualitative) data, and tabulations of descriptive statistics will be used to analyse continuous (quantitative) data.

Measurements (such as vital signs, or laboratory parameters) or AEs will be assigned to treatments (see [Section 4.1](#)) based on the concept of treatment emergent AEs. Therefore, measurements planned or AEs recorded prior to first intake of trial medication will be assigned to 'screening', those between first trial medication intake until the end of trial visit will be assigned to the treatment period, and those after the end of trial examination will be assigned to 'post-study'. These assignments including the corresponding time intervals will be defined in detail in the TSAP.

Adverse events will be coded using the Medical Dictionary for Regulatory Activities (MedDRA). Frequency, intensity and causal relationship of AEs will be tabulated by treatment, primary system organ class and preferred term. SAEs, AESIs (see [Section 5.2.2.1](#)) and other significant AEs (according to ICH E3) will be listed separately.

Laboratory data will be compared to their reference ranges. Values outside the reference range will be highlighted in the listings. Additionally, differences from baseline will be evaluated.

Vital signs or other safety-relevant data observed at screening, baseline, during the course of the trial and at the end-of-trial examination will be assessed with regard to possible changes compared to findings before start of treatment.

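### The protocol plans a descriptive ECG assessment and refers to an analysis of interval lengths, but SAP 7.8.4 specifies no ECG summary and SAP 4 declares no change

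*SAP*

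**What the plan says.** **Protocol.**
- Section 5.2.1 names one primary safety endpoint (subjects with drug-related AEs). It then lists further criteria, among them AEs, laboratory tests, 12-lead ECG and vital signs.
- Section 7.3.3 takes the 5.2.1 list as the scope of the safety evaluation and compares each active group descriptively with pooled placebo. For continuous data, "tabulations of descriptive statistics will be used to analyse continuous (quantitative) data". Vital signs and other safety data "will be assessed with regard to possible changes compared to findings before start of treatment".
- The synopsis, under statistical methods, states: "Descriptive statistics will be calculated for all endpoints". Section 7.1.1 describes the primary objective as pursued "by using descriptive statistics for all endpoints comparing active dose groups to placebo". Section 7.2 says of the safety variables that "they will be described in their entirety and evaluated by descriptive statistical methods".
- Section 5.2.4 contains this rule: "Unscheduled ECGs will not be included into the statistical analysis of interval lengths". For eligibility and for cardiac safety during the study, it says that "the QT and QTcB values generated by the ECG machines or their manual corrections by the investigators will be used".

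**SAP.**
- Section 7.8.4, in full: "ECG data will not be listed but clinically relevant abnormal findings will be reported as AEs".
- Sections 7.8.2 and 7.8.3 specify descriptive statistics for laboratory data and vital signs.
- Section 6.1 defines study phases for AEs, laboratory tests and vital signs. Section 6.7 defines a baseline for laboratory data and vital signs. Neither names ECG.
- Section 7.8 says in general that the safety analysis follows the protocol. Section 4 declares no change to the planned analysis.

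**The concern.** The rule in protocol 5.2.4 that keeps unscheduled ECGs out of the interval analysis has a purpose only if scheduled ECGs are analysed. The final SAP, which is meant to supply the detail, does not say how. It names no ECG parameter, time point, baseline, phase or display.

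The primary objective is safety and tolerability, and the escalation stop in protocol 3.3.4.2 uses a QTc change from baseline. If the programmers follow SAP 7.8.4 as written, an interval change reaches the report only when the investigator judges it clinically relevant and records it as an AE. A shift across a dose group made up of individually unremarkable changes would appear nowhere, and the active groups could not be compared with placebo on the intervals the protocol refers to. The statement in SAP 4 would then be wrong.

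**Working it through.** **1. Safety criteria side by side.** Laboratory tests, 12-lead ECG and vital signs stand as separate items in the same protocol list.

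| Criterion (protocol 5.2.1) | Phase in SAP 6.1 | Baseline in SAP 6.7 | Relevant findings go to AEs | Descriptive statistics specified |
|---|---|---|---|---|
| Laboratory tests | yes | yes | yes | yes (7.8.2) |
| Vital signs | yes | yes | yes | yes (7.8.3) |
| 12-lead ECG | no | no | yes | none (7.8.4) |

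The AE route is common to all three rows, so in the SAP's own scheme it does not replace a summary. ECG is the only one of the three without one.

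**2. How much data is involved.** ECG times come from the flow charts.
- IV, post-dose: 1:30, 2, 6, 12, 24 and 48 h, Days 8, 22 and 29, end of trial = 10.
- SC, post-dose: 2, 6, 12, 24 and 48 h, Days 8, 22 and 29, end of trial = 9. The SC end-of-trial row is garbled in the available text, but protocol 5.2.5.2 includes an ECG at that examination.

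Each of the four groups has 6 active and 2 placebo subjects.
- Each IV active group: 6 × 10 = 60 ECGs.
- SC active group: 6 × 9 = 54.
- Placebo: 6 × 10 + 2 × 9 = 78.
- Post-dose total: 3 × 60 + 54 + 78 = 312. Adding 32 pre-dose gives 344.
- Change-from-baseline cells: 3 × 10 + 9 = 39 active, plus 10 pooled placebo = 49.

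**3. How precise the tables would be.** The documents give no SD for change in QTc. I assume 10–15 ms, with 20 ms as a wide case. The 95% half-width for a difference in mean change is t × SD × √(1/n₁ + 1/n₂).

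| Comparison | n | t (df) | SD 10 | SD 15 | SD 20 |
|---|---|---|---|---|---|
| One active group v pooled placebo | 6 v 8 | 2.179 (12) | 11.8 ms | 17.7 ms | 23.5 ms |
| One IV group v placebo at 1:30 h, where only IV subjects have an ECG | 6 v 6 | 2.228 (10) | 12.9 ms | 19.3 ms | 25.7 ms |
| All active v placebo | 24 v 8 | 2.042 (30) | 8.3 ms | 12.5 ms | 16.7 ms |

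For example, 6 v 8 at SD 10: 2.179 × 10 × √(1/6 + 1/8) = 2.179 × 10 × 0.540 = 11.8 ms. A 10 ms shift in one dose group lies inside these limits. The value of the tables is therefore complete descriptive reporting, not detection of small effects.

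**The case against.** The best defence is that the documents do not strictly conflict. SAP 7.8.4 rules out a listing, not a summary. The next section, 7.8.5, excludes both listing and analysis for physical examination, so the authors could have done the same here. With SAP 7.8 deferring to the protocol, SAP 4 could then be true. This stands in part: an ECG table is not forbidden. But the protocol specifies no ECG parameters, displays or time points that SAP 7.8 could import, and protocol 7.3.3 itself leaves the detailed assignment of measurements to the SAP. The deferral therefore produces no table, and if it is meant to preserve the analysis, 7.8.4, 6.1 and 6.7 still need completing.

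A second point is that the protocol's commitment is general. ECG is a further criterion, not the primary endpoint. The interval analysis is mentioned once, inside an exclusion rule, and the change-from-baseline sentence does not name ECG. That is correct, and it limits the weight of the finding. Laboratory tests and vital signs have the same standing, however, and both are summarised.

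A third point is that parts of the SAP are blacked out. Section 7.8.4 is intact, so the conclusion about it is secure, but the statement that no ECG table is specified can be made only of the visible text.

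**Conclusion.** The concern holds and should be fixed. The protocol brings ECG within its descriptive safety evaluation and refers to an analysis of interval lengths. The visible SAP specifies none, and SAP 4 declares no change. This is either an undeclared omission or an ambiguity, and both need correcting. If 7.8.4 is followed as written, the SAP 4 statement is wrong.

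The consequence is limited. None of the 49 group-by-time cells (about 312 post-dose ECGs) is specified for reporting. The primary endpoint, the PK endpoints and the escalation stop are unaffected, and changes judged clinically relevant still reach the AE tables. The counts rest on the flow charts and full attendance. The half-widths rest on the assumed SD and do not bear on whether the documents disagree.

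**What to change.** **Preferred.**
- In SAP 7.8.4, specify descriptive statistics for the recorded ECG intervals, using the set already fixed in SAP 7 (N, mean, SD, min, median, max). Cover at least heart rate, QT and the QTcB that protocol 5.2.4 uses.
- Show baseline, each planned time and change from baseline, by active dose group and pooled placebo, on the treated set, from scheduled ECGs only.
- Add ECG to the phases in SAP 6.1 and to the baseline definition in SAP 6.7.

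**Alternative.** If the omission is intended, or the interval values are not in the database, say so in SAP 4 and justify the departure from the protocol.

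**Optional.** A QTcF table, an individual listing and threshold counts. Any count tied to the escalation stop should use the protocol's own joint criterion: QTc increase above 60 ms, together with absolute QT or QTc above 500 ms, confirmed by a repeat ECG.

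**Cost.** SAP wording and a few tables, with no new procedure or subject, provided the values were captured. The documents do not show that they were: protocol 5.2.4 has ECGs evaluated from local printouts, and protocol 5.2.3 describes electronic transfer for laboratory data only. If they were not captured, the cost is one paragraph in SAP 4.

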7.8.5 Others

Physical examination

Physical examination findings will be reported as relevant medical history/baseline condition (i.e., a condition already existent before intake of study drug) or as AE and will be summarised as such. No separate listing or analysis of physical examination findings will be prepared.

10. HISTORY TABLE

Table 10: 1 History table

Version	Date (DD-MMM-YY)	Author	Sections changed	Brief description of change
Initial	22-MAY-17		None	This is the initial TSAP with necessary information for trial conduct.
Final	01-FEB-18		Section 5, 6 and 7	Details for analysis are specified.
